5.2 Baseline characteristics

Baseline characteristics of participants will be presented by allocation group and follow-up 1 and 2 completion. Continuous variables will be presented including the total number, mean (SD), median (where data is not normally distributed), min, max and proportion missing. Categorical variables will be presented as total number (%) in each category. Table A1 shows the variables which will be collected at baseline for all women and their descriptive summaries.

5.3 Intention to treat

The main analyses will follow the intention to treat (ITT) principle. All participating women will be analysed by the group they were originally randomised into. Any woman randomised into the control group will be analysed as in the control group unless she requests removal from the study altogether. Furthermore, any woman randomised into the intervention group will be analysed as receiving the intervention even if she requests withdrawal from the intervention to receive standard of care. Women will be analysed as part of the pregnancy circle they were allocated to unless they join another circle prior to having attended any session in the allocated circle. This does not violate ITT since participants are still included in the analysis in the allocated treatment arm.

5.4 Withdrawals and loss to follow up

Women who choose to discontinue the group care will remain in the trial receiving standard of care and will be included in all analyses under the intention to treat principle. However, if a woman wishes to fully withdraw from the study the decision will be recorded, the withdrawal will be tabulated, and no further data will be collected. Moreover, women who withdraw before delivery will be excluded from the main analyses. However, we will still analyse their baseline data if available as stated in the protocol.

Women who have not been recorded as fully withdrawn and for whom no routine birth data is available are followed up with the Trusts by the trial team to seek their data. If unsuccessful, the participant is considered lost to follow up.

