3.1 Timing of outcome measures

Data on the various outcome measures used in this study will be collected either at baseline (recruitment; during the first antenatal booking appointment/first dating-scan appointment), first follow-up (35-weeks gestation), birth (routine maternity data) or second follow-up (3-months postnatal) or a combination of these time points. The table below shows the outcomes, the validated scales/measures which are being used where appropriate, and the specific time points when outcome data will be collected.

Outcome measure and data collection timing

Outcome	Validated measure (where applicable)	Baseline	First follow up - 35 weeks gestation	Birth – routine maternity data	Second follow up - 3 months postnatal
Live baby				√	
Born at term				✓	
Appropriate weight for gestational age	GROW centile >9.99 & <90.01			✓	
Not admitted to a Neonatal Care Unit				✓	
Spontaneous vaginal delivery (SVD)				√	~
Women's empowerment	Pregnancy-related Empowerment Scale (PRES)		√		
Women's satisfaction with maternity care	Friends and family test		✓		√
Attendance at antenatal care			√	√	
Social support	The Duke-UNC Functional Social Support Questionnaire	✓			✓
Self-efficacy	Pearlin Mastery Scale	√	✓		√

Prenatal stress	Revised prenatal distress scale	√	√		
Caesarean delivery				√	√
Infant birth weight (g)				1	
Place of birth				√	
Breast feeding initiation					✓
Breast feeding continuation and exclusivity					√
Postnatal depression	Edinburgh Postnatal Depression Scale (EPDS)				√
Health Literacy	Health Literacy Questionnaire (HLQ) (1 domain)		√		
Postnatal symptoms	(NPEU checklist)				✓
Emotional wellbeing	Short Warwick- Edinburgh Mental Wellbeing Scale (SWEMWBS)	√	✓		✓
Health related quality of life	EQ5D-5L	√	√		✓
Continuity with care			√		
Choice in care			√		√
Involvement in care					√
Preparedness for labour and birth			√		√
Confidence in caring for baby after birth					√
Immunisation					√

Additional			,
measures of		,	√
satisfaction with		V	
care			

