3.2 Primary outcome

The "healthy baby" composite consists of the following 4 components:

- 1. Live baby (i.e. no pregnancy loss before 24 completed weeks, no stillbirth after 24 completed weeks of pregnancy and no neonatal death within 28 days of the birth)
- 2. Born at term (≥ 37 weeks + 0 days)
- 3. Appropriate weight for gestational age (GROW centile >9.99 & <90.01)*
- 4. Not admitted to a neonatal care unit (which includes Intensive Care Unit, SCBU and High Dependency Unit, but NOT transitional care)

A baby is considered a "healthy baby" only if the answer to all above questions is "yes", otherwise "no" (binary outcome measure). The primary outcome will be considered missing if any of its components are missing apart from the following exception: If Live baby is recorded as 'no' then the healthy baby outcome is 'no' regardless of whether other components are missing.

* The GROW centile macro version 8.0.6.2 will be used for component 3. Appropriate weight for gestational age. It is multidimensional and includes: maternal height and weight, ethnic origin, parity at booking, gestational age, baby alive (yes/no), baby gender and weight (g).

Note: at the grant application stage, the secondary outcome, spontaneous vaginal delivery (SVD) was defined as the primary outcome for the trial. However, following advice from and discussion with various stakeholders the "healthy baby" composite outcome was deemed a more suitable primary outcome for this project and chosen prior to commencement of the trial.

3.3 Secondary Outcomes*:

- 1. Spontaneous vaginal delivery (SVD)** defined as a woman who delivers vaginally (binary: for SVD, yes favoured)
- 2. Women's empowerment using pregnancy-related empowerment scale (continuous: sum of individual items with scores ranging from 16-64; higher scores are favoured)
- 3. Women's satisfaction with maternity care using *NHS* Friends and family test (continuous: score on one question with scores ranging from 1-5; lower scores favoured)
- 4. Breast feeding initiation (binary: did mother ever initiate breastfeeding, yes favoured --> however, possible different responses for descriptive analysis)
- 5. Mental wellbeing using Short Warwick-Edinburgh Mental Wellbeing Scale (continuous: total score ranges from 7-35, higher scores indicate higher positive mental wellbeing)

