5.5 General analysis principles

The analysis of primary, secondary, and, where possible, additional outcomes will be adjusted for the stratification factors which were used during randomisation, centre, and ability to speak English, only. All main analyses will be performed on a complete case basis (ignoring missing data) for the outcomes in question. A missing category will be created for the only covariate in the models "ability to speak English". The significance for statistical tests (alpha) will be 5%, all confidence intervals will be presented at the 95% level and all p-values will be two-sided. As the intervention arm includes group pregnancy circles, clustering will be accounted for in the intervention arm using pregnancy

circles as the units of clustering, while participants in the control arm will be modelled as a cluster size of one [1].

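### Section 5.4 excludes women by when they fully withdrew, not by whether the outcome is missing, so completed 35-week questionnaires are discarded

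*SAP*

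**What the plan says.** Section 5.4 treats two groups differently.

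- **Stopping group care only.** "Women who choose to discontinue the group care will remain in the trial receiving standard of care and will be included in all analyses".
- **Full withdrawal from the study.** "the decision will be recorded, the withdrawal will be tabulated, and no further data will be collected". As a further rule, "women who withdraw before delivery will be excluded from the main analyses. However, we will still analyse their baseline data if available". The sentence on baseline data refers to the protocol.

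Other sections that bear on the same women:

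- Section 5.3: "All participating women will be analysed by the group they were originally randomised into". The exception for leaving the study is written for one arm: "Any woman randomised into the control group will be analysed as in the control group unless she requests removal from the study altogether". The matching sentence for the intervention arm covers only withdrawal from the intervention.
- Section 5.5: "All main analyses will be performed on a complete case basis (ignoring missing data) for the outcomes in question".
- Section 3.1 places data collection after baseline at "first follow-up (35-weeks gestation), birth (routine maternity data) or second follow-up (3-months postnatal"). Three secondary outcomes are collected at 35 weeks: empowerment, the Friends and Family Test and SWEMWBS. So are additional outcomes such as prenatal distress and health literacy.
- Section 3.2: "If Live baby is recorded as 'no' then the healthy baby outcome is 'no' regardless of whether other components are missing".
- Section 5.8 defines the primary-outcome population by the protocol's exclusion list and the pandemic exclusions. It does not exclude women who fully withdraw.

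**The concern.** The exclusion is triggered by an event after randomisation and not by the absence of data. Section 5.5 already omits a woman from any analysis for which she has no outcome. The extra sentence in 5.4 can therefore change a result only by removing outcomes that were recorded.

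Two groups are exposed. The first is women who return the 35-week questionnaire and then leave the study before birth. The second, depending on interpretation, is women who leave after a pregnancy loss has been recorded.

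Participants and maternity staff know the allocation (4.3), so full withdrawal could differ between arms and could be related to how a woman feels about her care. The 35-week secondary outcomes measure just that: empowerment, satisfaction and wellbeing. Removing recorded answers from those women is an avoidable departure from the intention-to-treat commitment.

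**Working it through.** **1. Figures available.** The rule in 5.4 carries no figure, and no count of full withdrawals is given. Section 4.1.1 supplies planning values: 69% healthy in the control arm, a difference of 8 points (so 77%), 866 women per arm, and 10% drop-out in both arms.

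The planned total of 1732 reproduces closely:

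- 646 per arm for 69% against 77% (two-sided 5%, 90% power).
- Design effect in the intervention arm: 1 + ((1 + 1/8) × 8 − 1) × 0.05 = 1.40. Averaged over the arms: 1.20.
- 646 × 1.20 = 775.2, rounded up to 776. Then 776 / 0.90 = 862.2, rounded up to 863 per arm, or 1726 in total (0.3% below 1732).

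This figure does not depend on 5.4, and keeping recorded data does not alter it.

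**2. Where the rules diverge.**

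| Woman | Outcome | Under 5.5 (with 3.2) | Under 5.4 |
|---|---|---|---|
| Stops group care only | all | kept if recorded | kept |
| Withdraws fully at 20 weeks, no loss | all after baseline | missing | excluded |
| Completes 35-week questionnaire, withdraws fully at 37 weeks before birth | 35-week scales | **kept** | **excluded** |
| The same woman | birth outcomes | missing, as collection has stopped | excluded |
| Loss recorded, then withdraws fully | Healthy baby | **'no', kept** | **excluded or kept, depending on how *before delivery* is read** |

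The sections conflict outright in the third row and possibly in the last. Elsewhere the 5.4 sentence makes no difference. A woman with a loss is not sent the questionnaires (note to 3.3), so the last row concerns birth outcomes only.

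**3. What the size depends on (assumed inputs, not data from the SAP).**

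*35-week scales.* Let a share w of one arm's completers later withdraw, with a mean d standard deviations below the other completers. The full-arm mean is m − w × d, where m is the mean of those who stay. Excluding the withdrawers gives m, so the shift is w × d. With w = 2% and d = 0.25 it is 0.02 × 0.25 = 0.005 SD. With w = 10% and d = 0.5 it is 0.10 × 0.5 = 0.05 SD. If w and d are the same in both arms, the shifts cancel.

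*Recorded losses, if 5.4 is read as removing them.* Removing a share x of the intervention arm, all scored 'no', moves 0.77 to 0.77 / (1 − x):

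- x = 0.25% (about 2 of 866): +0.19 points
- x = 0.5% (about 4): +0.39 points
- x = 1% (about 9): +0.78 points
- x = 2% (about 17): +1.57 points

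These values assume removal in one arm only, which is the extreme case. With the same share removed from both arms the difference becomes 0.08 / (1 − x). At x = 2% that is 0.0816, a shift of 0.16 points.

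**The case against.** **The primary outcome would be missing anyway.** Section 5.9 takes it from an audit of maternity records after birth, and 5.4 stops collection at full withdrawal. This stands. For nearly all of these women the sentence costs the primary analysis nothing, and no rewording would recover their birth outcomes.

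**A loss need not fall under the rule.** A stillbirth after 24 weeks is ordinarily a delivery, and *before delivery* may mean before the pregnancy ended. Section 3.2 is also explicit on how a loss is scored. This stands in part: the point is an undefined term, not a demonstrated exclusion.

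**The protocol or consent may require the exclusion.** The baseline sentence cites the protocol, which is not shown. This cannot be ruled out. However, the SAP keeps these women's baseline data, so full withdrawal does not in itself oblige the trial to discard what it holds. Section 1.6 also makes the SAP prevail over earlier documents on analysis.

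**The scope is small and partly mitigated.** The window is the few weeks between the questionnaire and birth, and only full withdrawal counts. Outcome extractors are blinded (4.3), and 4.2 promises immediate disclosure of allocation only to women recruited in person. The exclusion is confined to the main analyses, and 5.16.1 imputes the primary outcome. All of this limits the effect. But 5.16.1 does not say whether withdrawn women are included, and its text covers the primary outcome, so it does not restore the 35-week scales.

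**Conclusion.** The point holds for the 35-week outcomes. On its literal wording, 5.4 discards recorded empowerment, satisfaction, wellbeing and additional scores that 5.5 and 5.3 would keep. For recorded pregnancy losses it is an ambiguity between 5.4 and 3.2 that should be settled before the analysts see allocations.

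The size cannot be computed from the SAP. It depends on how many women withdraw fully after the questionnaire or after a loss, on the balance between arms, and on how they differ from those who stay. The illustrative shifts above rest wholly on assumed values and are small when withdrawal is balanced.

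A reader might infer that the rule biases the primary outcome by removing every withdrawn woman, and might estimate that bias by assuming a lower healthy rate among them. The SAP does not support this. Such a calculation measures ordinary attrition, which would remain if 5.4 were corrected. Only a loss recorded before withdrawal is at issue for the primary outcome. Bias there is possible but not shown.

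**What to change.** Replace the exclusion sentence in 5.4 with:

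> A woman who fully withdraws contributes, in her randomised arm, every outcome recorded up to her withdrawal, including 35-week questionnaire outcomes and any recorded pregnancy loss (Healthy baby = no). Outcomes not yet recorded are treated as missing, and she is included in the multiple-imputation analysis of 5.16.1, unless she asked for her data to be removed.

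Apply the removal exception in 5.3 to both arms in the same terms. Tabulate full withdrawals by arm and by timing: before 35 weeks, between the questionnaire and birth, and after a recorded loss. The SAP already plans to tabulate withdrawals, so only the split is new.

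The cost is a short text change and a slightly larger table, with no new data, no further participants and no change to the sample size. The one precondition is to confirm that the protocol and consent terms on withdrawal allow use of data already held.

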5.5 General analysis principles

The analysis of primary, secondary, and, where possible, additional outcomes will be adjusted for the stratification factors which were used during randomisation, centre, and ability to speak English, only. All main analyses will be performed on a complete case basis (ignoring missing data) for the outcomes in question. A missing category will be created for the only covariate in the models "ability to speak English". The significance for statistical tests (alpha) will be 5%, all confidence intervals will be presented at the 95% level and all p-values will be two-sided. As the intervention arm includes group pregnancy circles, clustering will be accounted for in the intervention arm using pregnancy

circles as the units of clustering, while participants in the control arm will be modelled as a cluster size of one [1].

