- 6. Live baby (i.e. no pregnancy loss before 24 completed weeks, no stillbirth after 24 completed weeks of pregnancy and no neonatal death within 28 days of the birth) using health records (binary: yes favoured)
- 7. Born at term (37 weeks + 0 days and above) using health records (binary: yes favoured)

- 8. Appropriate weight for gestational age (GROW centile >9.99 & <90.01) using health records (binary: yes favoured)
- 9. Not admitted to a neonatal care unit (which includes Intensive Care Unit, SCBU and High Dependency Unit, but NOT transitional care using health records binary: yes favoured)
- * Those for whom the primary outcome composite healthy baby variable is 'no' will inevitably have a lower response rate for the first follow up questionnaire. This is because the composite includes whether a baby is alive and born at term (i.e. at 37+ weeks gestation). Participants who have experienced pregnancy loss (baby alive = no) are not sent the first (or second) follow up questionnaire. Participants who deliver prematurely (<35 weeks) will not have had the opportunity to complete the first follow up questionnaire before delivery and are unlikely to complete it after. Analyses of variables collected via the follow up questionnaire, such as empowerment, satisfaction with care, self-efficacy, pre-natal stress, health literacy and emotional well-being, will acknowledge the exclusion of these groups, particularly if it is found that the intervention does have a significant effect on the primary outcome.
- ** Routine data will be used as the default source of data for SVD. We will use second follow-up SVD data only if routine data values for a participant are missing.

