Secondary and additional outcomes providing continuous responses, such as a total score on any of the scales being used, will be analysed by assessing difference of means between intervention and control groups. This will be analysed using a partially nested mixed-effects model with heteroskedastic error terms with the Satterthwaite approximation for degrees of freedom to avoid upward bias of the type-I error rate (2). The English level will again be included as covariate in these models. The resulting model will estimate a difference of means between the intervention and control arms of the study. Specifically, let y be the continuous outcome, i is the mother participant indicator, j is the pregnancy indicator, t is the intervention indicator (0 = usual care, 1 = pregnancy circle), θ is the intervention effect, θ_0 is an intercept term, and θ_k represents fixed effects for English level. Then,

$$y_{ij} = \beta_0 + \theta t_{ij} + \beta_k + u_i t_{ij} + r_{ii} (1 - t_{ij}) + \epsilon_{ij} t_{ij} + v_1$$

where $u_j \sim N(0, \sigma^2_u)$ is a random-effects term representing between-cluster (pregnancy circle) variation in the clustered intervention arm, $r_{ij} \sim N(0, \sigma^2_r)$ represents individual-level variation in the

non-clustered control arm, $\epsilon_{ij} \sim N(0, \sigma^2_{\epsilon})$ represents individual-level variation in the clustered intervention arm and $v_i \sim N(0, \sigma^2_w)$ is the random effect representing between-site variation.

Analysis of categorical outcomes

For categorical outcomes, proportions by intervention group and test of between group difference without covariate adjustment will be presented.

Strategy for analysis of primary outcome if model fails to converge

In case the analysis of the primary outcome described above fails to converge, the following sequential strategy will be employed (starting at 1).

	Change from previous strategy
1	Try an alternative estimation algorithm, such as the
	QR decomposition in meqrlogit, rather than Stata's
	default melogit function.
2	Change the number of integration (quadrature)
	points for all levels using intpoints() command
3	Try an alternative integration method other than
	mean-variance adaptive Gauss-Hermite
	quadrature like Laplace for example.
4	Remove covariate English speaking level from the
	model.
5	Analysis using model, not assounting for clustering
5	Analyse using model, not accounting for clustering
	within intervention groups.

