5.10 Missing Data

For the analysis of the primary and secondary outcomes we assume that the data are missing completely at random. Sensitivity analysis to this assumption will be explored in sensitivity analyses for the primary outcome using multiple imputation (6). Further details are provided in the sensitivity analysis section. Moreover, we will only consider the primary outcome for women in the situation where all of its components are non-missing (i.e. available complete-case analysis).

The primary outcome is comprised of routine birthing data. The study team's commitment to attempt to locate and follow-up women with missing data has contributed to decrease this proportion as much as possible.

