8.4 Dummy result tables

Table 1: Baseline Characteristics of recruited women in REACH*

Baseline characteristics	Usual care (N=)	Pregnancy circle (N=)	Total (N=)
Age (years)			
N of non-missing values			
Mean (sd) [IQR]			
Ethnicity - N (%)			
White-British			
White-Irish			
Other-White			
Black or Black British-Caribbean			
Black or Black British-African			
Black or Black British-other Black			
Asian or Asian British-Indian			
Asian or Asian British-Pakistani			
Asian or Asian British-Bangladeshi			
Asian or Asian British-Chinese			
Asian or Asian British-Other Asian			
Mixed-White & Black Caribbean			
Mixed-White & Black African			
Mixed-White & Asian, Mixed-Other			
Other - Arab, Any other ethnic group			
Missing			
What is your main language - N (%)			
English			
Other			
Missing			
How well can you speak English - N (%)			
Very well or well			

PCTU_TEM_ST_02
Statistical Analysis Plan template V 3.0

Study REACH WP3
Document version 1.0

No. allocations at the Principle
Not well or I do not speak any English
Missing
What is your highest educational qualification?
- N (%)
Don't have any
GCSE or similar (exams after 5 years of
high school)
Vocational qualifications (e.g. NVQ, BTEC)
A level or similar (exams after 7 years of
high school)
University undergraduate degree
Postgraduate degree
Missing
Attendance to antenatal care - N (%)
Woman didn't miss any session
Missed one or two
Missed 3 or more
Missed all sessions
Can't remember
Missing
Revised prenatal distress scale
N of non-missing values
Mean (sd)
[Min, max]
IQR
Emotional Wellbeing (SWEMWBS)
N of non-missing values
Mean (sd)
[Min, max]
IQR
*

^{*}This table will be produced by follow up completion (35 weeks pregnant and 3 months post-partum)

Table 2: Results for analysis of primary, secondary and additional binary outcomes

	Number in		Summary	measure	Treatmer	nt effect		
	analy							
Outcome	Usual care	PC*	Usual care	PC*	Odds ratio	Risk diff.	p-value	ICC**
	n (%)	n (%)	% of yes	% of yes	[95% CI]	[95% CI]		[95 % CI]***
Healthy baby								
Baby alive								
Gestation at								
birth >36wk								
Appropriate								
weight for								
gestational age								
Admitted to a								
neonatal care								
unit								
Spontaneous								
vaginal delivery								
without								
instruments								
Breast feeding								
initiation								
Breast feeding								
continuation at								
Month 3 pp								
Postnatal								
depression at								
Month 3 pp								

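### Four questionnaire scales measured at baseline are analysed without their baseline score, and the missing-completely-at-random assumption for the secondary questionnaire outcomes conflicts with the SAP's own account of non-response

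*SAP*

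**What the plan says.** **Covariates.** SAP 5.5 states that primary, secondary and, where possible, additional outcomes are "adjusted for the stratification factors which were used during randomisation, centre, and ability to speak English, only". On missing covariates it adds: "A missing category will be created for the only covariate in the models", meaning ability to speak English. For continuous outcomes, 5.9 says: "The English level will again be included as covariate in these models". The equation there has an intercept, treatment, English level, circle, site and residual terms, and nothing else.

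**Baseline data.** The table in 3.1 ticks baseline for SWEMWBS, the Duke-UNC social support questionnaire, the Pearlin scale and the revised prenatal distress scale. SWEMWBS is secondary outcome 5 (3.3). The other three are additional outcomes 1 to 3, which 3.4 presents as mainly exploratory. The empowerment scale and the Friends and Family test have no baseline measurement.

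**Missing data.** For the primary and secondary outcomes, 5.10 says "we assume that the data are missing completely at random", and 5.5 makes all main analyses complete-case. The footnote to 3.3 says that women whose healthy-baby outcome is no "will inevitably have a lower response rate for the first follow up questionnaire". Women with a pregnancy loss are sent neither questionnaire, and those delivering before 35 weeks are unlikely to complete the first. The footnote promises to acknowledge this in the analyses. Multiple imputation in 5.16.1 covers the primary outcome, and dummy Table 11 adds spontaneous vaginal delivery. No questionnaire score is imputed.

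**The concern.** A woman's earlier score on an instrument is usually among the best predictors of her later score on it. The plan collects that score and then rules it out with the word only, giving no reason. At stake is the width of the confidence interval for one secondary and three exploratory outcomes. Respondents may also differ between arms at baseline, by chance or through attrition, and the model could not correct for it.

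The missing-data statement raises a different question. Missing completely at random means that response is unrelated to anything about the woman. The footnote says response depends on how the pregnancy went, which is what the trial aims to change. If the intervention works, the two arms lose different proportions of women to this mechanism.

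**Working it through.** **1. The plan's own figure.** The SAP gives no power or sample size for any questionnaire outcome. Its 866 per arm (4.1.1) is for the healthy-baby composite. It is checked here only because its design effect is borrowed below.
- Design effect in the intervention arm, mean circle size 8, Poisson variation (CV² = 1/8), ICC 0.05: 1 + [(1 + 1/8) × 8 − 1] × 0.05 = 1.40.
- Per arm, 69% v 77%, 90% power, two-sided 5%: 10.507 × (0.2139 + 1.40 × 0.1771) / 0.08² = 758; divided by 0.90 for drop-out, 842.
- Two other standard variants give 855 and 861. All are within 3% of 866, so the figure reproduces. It neither supports nor weakens the present point.

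**2. Precision lost by omitting baseline.** Let r be the baseline-to-follow-up correlation (assumed; the SAP gives none).
- Upper bound: all variance falls by the factor 1 − r², and the equivalent sample multiplier is 1/(1 − r²).
- Cautious version: the baseline score explains only individual-level variance. With the borrowed ICC, the intervention-arm 1.40 splits into 0.95 (individual) and 9 × 0.05 = 0.45 (circle). The control arm contributes 1. The multiplier is 2.40 / [(1 − r²) + 0.95(1 − r²) + 0.45].

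| r | upper bound | SE reduction | cautious | SE reduction |
|---|---|---|---|---|
| 0.3 | 1.10 | 5% | 1.08 | 4% |
| 0.4 | 1.19 | 8% | 1.15 | 7% |
| 0.5 | 1.33 | 13% | 1.25 | 11% |
| 0.7 | 1.96 | 29% | 1.66 | 22% |

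Cautious case at r = 0.5: 0.75 + 0.7125 + 0.45 = 1.9125, and 2.40/1.9125 = 1.25.

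To put this in SD units, take 866 per arm and 60% response (assumed): 519.6 responders per arm, 4.8 per circle, design effect 1.24. Without baseline, the difference detectable with 90% power is 3.2415 × √(2.24/519.6) = 0.213 SD. At r = 0.5 it falls to 0.184 SD in the upper-bound case. In the cautious case it is 3.2415 × √(1.7525/519.6) = 0.188 SD, where 1.7525 = 0.75 + 0.7125 + 0.29.

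**3. The two missing-data statements side by side.** Section 5.10 says missingness in secondary outcomes is unrelated to anything. The footnote to 3.3 says it follows from pregnancy loss and early delivery, and lists empowerment, satisfaction and emotional well-being among the affected outcomes. Both cannot hold for those three secondary outcomes.

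**4. How much bias that could cause.** Assume healthy-baby rates of 69% and 77%, 70% response among women with a healthy baby, scores 0.3 SD lower otherwise, and no other treatment effect. The true difference is 0.3 × (0.31 − 0.23) = 0.024 SD. Let q be response among the remaining women. Their share of respondents is 0.31q/(0.31q + 0.69 × 0.70) in control and 0.23q/(0.23q + 0.77 × 0.70) in intervention.
- q = 50%: shares 0.243 and 0.176, estimated difference 0.020 SD, bias 0.004.
- q = 30%: shares 0.161 and 0.113, estimated difference 0.014 SD, bias 0.010.
- q = 0%: estimated difference 0, bias 0.024.

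The bias is toward the null throughout.

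**The case against.** Adjusting for stratification factors alone is pre-specified, applied consistently and valid under randomisation. A reader might infer that omitting the baseline score biases the treatment comparison. It does not, and nothing in the SAP suggests it. The cost falls on one of nine secondary outcomes and three exploratory ones. This objection stands and limits the weight of the point, but it is no reason to leave collected data unused.

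A reader might also infer that the contradicted assumption covers all four scales. Section 5.10 names primary and secondary outcomes, so of the four it reaches only SWEMWBS. The other three fall under the complete-case rule of 5.5 with no stated mechanism. Social support is followed up only at 3 months, so the sentence about the first questionnaire does not touch it, although non-mailing after pregnancy loss does.

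Nor would the baseline score by itself repair the assumption. The footnote attributes non-response to events after randomisation, and two of the three affected secondary outcomes have no baseline value.

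Finally, the SAP is open about the mechanism. Section 5.2 and the footnote to Table 1 present baseline characteristics, including SWEMWBS and prenatal distress, by follow-up completion. That would reveal attrition related to baseline score. It would not change the estimate or test its sensitivity.

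**Conclusion.** Both parts hold, within limits. Omitting the same-instrument baseline score for four scales loses precision that costs nothing to recover: at r = 0.5, an equivalent sample 1.25 to 1.33 times as large (SE 11% to 13% smaller). The full 1/(1 − r²) gain is an upper bound, because a baseline score may not reduce variation between circles. These sizes rest on an assumed correlation and an ICC borrowed from the primary outcome. Missing baseline values would reduce the gain, and fewer responders per circle would narrow the gap between the two versions.

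The missing-data wording in 5.10 contradicts the footnote to 3.3 for empowerment, Friends and Family and SWEMWBS. It would be tempting to conclude that these comparisons are seriously distorted. The assumed scenario gives only 0.004 to 0.024 SD toward the null, and the SAP has no response rates from which to argue for more. Precision is the main gain; consistency of the stated assumption is the second.

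**What to change.** 1. **Sections 5.5 and 5.9.** For SWEMWBS, social support, mastery and prenatal distress, add the baseline score of the same instrument as a fixed covariate. State one rule for missing baseline values, such as mean imputation or a missing indicator, so that no respondent is lost.

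2. **Section 5.10.** For the secondary questionnaire outcomes, replace the missing-completely-at-random statement. Treat women with pregnancy loss as outside the questionnaire population, and label this as conditioning on a post-randomisation event. Define the population separately for 35 weeks and 3 months: a woman with an early live birth belongs to the 3-month population, since only loss stops the second questionnaire. For the rest, assume missing at random given allocation, site, English level, gestation or birth outcome, and baseline score where one exists.

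3. **Section 5.16.1.** Extend multiple imputation to the empowerment scale, Friends and Family and SWEMWBS on that basis, and add rows to Table 11. Gestation and birth outcome belong in the imputation model as auxiliary variables, which the section already allows for. They should not enter the analysis model, because they follow randomisation. If almost no early deliverers return the first questionnaire, say that imputing for them is extrapolation.

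The cost is SAP wording, one term in four models and one more sensitivity table. The baseline scores and birth data are already collected. The amendment should be dated before unblinded results are seen; after that, it should be labelled post hoc.
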